6.2 Planned Efficacy Analyses for Each Analysis Dataset

A list of contents of efficacy analyses described in the Statistical Methods section (Section 8.0) is provided below. The list of analyses will be performed for all three analysis datasets separately. Data will not be pooled across studies.

- Complete remission (CR) rate (Analysis datasets 1 - 3)
- Complete remission with partial hematologic recovery (CRh) rate (Analysis datasets 1 - 3)
- CR + CRh rate (Analysis datasets 1 - 3)
- CR + CRh rate by the initiation of Cycle 2 (Analysis datasets 1 - 3)
- Time to the first response of CR + CRh (Analysis datasets 1 - 3)
- Time to best response of CR + CRh (Analysis datasets 1 - 3)
- Duration of CR (Analysis datasets 2 - 3)
- Duration of CR + CRh (Analysis datasets 1 - 3)
- CR + CRi rate (Analysis datasets 2 - 3)
- CR + CRi rate by the initiation of Cycle 2 (Analysis datasets 2 - 3)
- Time to the first response of CR + CRi (Analysis datasets 2 - 3)
- Time to best response of CR + CRi (Analysis datasets 2 - 3)
- Duration of CRi (Analysis datasets 2 - 3)
- Duration of CR + CRi (Analysis datasets 2 - 3)
- Objective Response Rate (CR + CRi + PR) (Analysis datasets 2 - 3)
- Overall survival (OS) (Analysis datasets 2 - 3)

- Post baseline RBC/Platelet transfusion independence and duration of post baseline RBC/Platelet transfusion independence (Analysis datasets 1 - 3)
- Time to first RBC/platelet transfusion (Analysis datasets 2 - 3)
- Time to the first recurrent RBC/platelet transfusion (Analysis dataset 2 - 3)
- Time to first Grade 3 or above TEAE hemorrhage event (SMQ narrow) (Analysis datasets 2 - 3)
- Time to first Grade 3 or above TEAE SOC of "infections and infestations" event (Analysis datasets 2 - 3)
- Time to first hospitalization due to SAE (Analysis datasets 2 - 3)

7.0 Analysis Conventions

Definition of Study Drug

Unless otherwise specified, the study drug in this document refers to

- Venetoclax and HMA (Study M14-358)
- Venetoclax and LDAC (Study M14-387)

Definition of Last Dose of Study Drug + 30 Days

Last dose of study drug + 30 days is defined as the last of dose of venetoclax, HMA, or LDAC + 30 days on or prior to data extraction dates.

Definition of Baseline

Unless otherwise stated, baseline for a given variable will be defined as the last non-missing value for that variable obtained prior to the first dose of any component of study drug.

Definition of Study Day

Study Day is defined as the number of days since (positive numbers) or prior to (negative numbers) the first dose of study drug. The day of the first dose of study drug is defined as Study Day 1, while the day prior to the first dose of study drug is defined as Study Day –1; there is no Study Day 0.

Definition of Final Observation

The final observation is defined as the last non-missing observation collected.

Full Analysis Set

The full analysis set includes all subjects who received at least one dose of venetoclax.

Safety Analysis Set

The safety analysis set includes all subjects who received at least one dose of venetoclax.

8.0 Statistical Methods

Unless otherwise specified, all summaries/analyses of three analysis datasets will be presented separately. Disposition, demographic, prior and concomitant medication, prior disease history including AML, and study drug exposure summary will be performed as described in the safety SAP.

8.1 Efficacy Analyses

Unless otherwise specified, all summaries/analyses of efficacy data will be presented for all treatment groups of the analysis datasets 1 – 3 specified in [Table 3](#) separately. There will be no pooled analyses across the three analysis datasets. All subjects who have received at least one dose of venetoclax will be included in the efficacy analyses. Unless otherwise stated, the data cutoff date will be applied to efficacy analyses for Study M14-358 and Study M14-387 (Analysis dataset 2 - 3).

8.1.1 Complete Remission (CR) Rate

Complete Remission (CR) is a response based on investigator report using modified IWG criteria for AML.

Complete Remission (CR) rate will be defined as the proportion of subjects who achieve a complete remission at any time point during the study per the modified IWG criteria for AML. Subjects who never achieve CR or have no IWG disease assessment will be considered to be non-responders in the calculation of CR rate. In addition to the CR rate, the 95% confidence interval for CR rate based on the binomial distribution (Clopper-Pearson exact method) will be provided. The disease assessment collected after the post-treatment therapy will be excluded.

8.1.2 CRh Rate

CRh (Complete remission with partial hematologic recovery) is a derived response based on bone marrow blast and hematology lab values. A Subject achieves a CRh when meeting the following criteria:

- Bone marrow with < 5% blasts and
- Peripheral blood neutrophil count of $> 0.5 \times 10^3/\mu\text{L}$ and
- Peripheral blood platelet count of $> 0.5 \times 10^5/\mu\text{L}$ and
- A 1 week (≥ 7 days) platelet transfusion-free period prior to the hematology lab collection.

For a bone marrow sample collected before the last cycle of study treatment, the hematology lab results collected from the date of the bone marrow sample collection up to the Day 1 of a subsequent cycle of study treatment will be used for CRh analysis.

For a bone marrow sample collected during or after the last cycle of study treatment, the hematology lab results collected within 14 days after bone marrow sample collection date will be used for CRh analysis.

CRh rate will be defined as the proportion of subjects who achieve CRh as the best response at any time point during the study. Subjects who never achieve CRh or have not had disease assessment or hematology data will be considered to be non-responders in the calculation of CRh rate. In addition to the CRh rate, the 95% confidence interval for CRh rate based on the binomial distribution (Clopper-Pearson exact method) will be provided. The disease assessment collected after the post-treatment therapy will be excluded for above analyses.

8.1.3 CR + CRh Rate

CR + CRh rate will be defined as the proportion of subjects who achieve CR or CRh at any time point during the study. Subjects who never achieve CR/CRh or have no disease assessment will be considered to be non-responders in the calculation of CR + CRh rate. In addition to the CR + CRh rate, the 95% confidence interval for CR + CRh rate based on the binomial distribution (Clopper-Pearson exact method) will be provided.

The time to the 1st response of CR + CRh is defined as number of days from the 1st date of study drug to the 1st response of CR + CRh. The time to the best response of CR + CRh is defined as number of days from the 1st date of study drug to the 1st date of best response of CR + CRh.

The medians and ranges of time to the 1st response of CR + CRh and time to the best response of CR + CRh for all subjects, as well as for subjects with best response CR or best response of CRh will be summarized.

The disease assessment collected after the post-treatment therapy will be excluded for above analyses.

8.1.4 CR + CRh Rate by Initiation of Cycle 2

CR + CRh rate by initiation of Cycle 2 will be defined as the proportion of subjects who achieve CR or CRh by initiation of Cycle 2 of study treatment. Subjects who never achieve CR or CRh or have not had disease assessment by initiation of Cycle 2 will be

considered to be non-responders in the calculation of CR + CRh rate by initiation of Cycle 2. In addition to the CR + CRh rate by initiation of Cycle 2, the 95% confidence interval for CR + CRh rate by initiation of Cycle 2 based on the binomial distribution (Clopper-Pearson exact method) will be provided.

The disease assessment collected after the post-treatment therapy will be excluded for above analysis.

8.1.5 Duration of CR

Duration of CR is defined as number of days from date that subject achieved CR to the first date of relapse, clinical disease progression or death due to disease progression, whichever occurred earliest. If a subject is still responding at the data cutoff date, then the subject's data will be censored. The disease assessment data after the onset of any post-treatment therapy will not be included in the duration of CR analysis. The detailed censoring rule is described in [Table 4](#). For each analysis dataset, the distribution of duration of CR will be estimated using Kaplan-Meier methodology. Median duration of CR with the corresponding 95% CI will be provided from Kaplan-Meier estimation.

Table 4. Event/Censor and Corresponding Event/Censor Time for Duration of CR or CR + CRh

Situation	Event/Censor	Event Time/Censor Time
IWG disease progression (PD) or Clinical disease progression (CPD) on or prior to any post-treatment therapy and data cutoff date, whichever is earliest	Event	Earliest PD date
Death due to disease progression on or prior to data cutoff date regardless whether it occurred after any new post-treatment	Event	Death date
Neither PD nor CPD nor Death due to disease progression and without post-treatment therapy on or prior to the data cutoff date	Censor	Last disease assessment date (bone marrow or hematology lab collection date) on or prior to the data cutoff date
Neither PD nor CPD nor Death due to disease progression but having post-treatment therapy on or prior to the data cutoff date	Censor	Start of post-treatment therapy

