8.1.6 Duration of CR + CRh

Duration of CR + CRh is defined as number of days from date that subject achieved CR + CRh to the first date of relapse, clinical disease progression or death due to disease progression, whichever occurred earliest. If a subject is still responding at the data cutoff date, then the subject's data will be censored. The disease assessment data after the onset of any post-treatment therapy will not be included in the duration of CR + CRh analysis. The detailed censoring rule is described in [Table 4](#). For each analysis dataset, the distribution of duration of CR + CRh will be estimated using Kaplan-Meier methodology. Median duration of CR + CRh with the corresponding 95% CI will be provided from Kaplan-Meier estimation. Duration of CR + CRh will be summarized for all subjects, subjects achieving CR, and subjects achieving CRh.

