8.1.11 Additional Sensitivity Analyses of Efficacy Variables

Duration of Response

Sensitivity analyses for duration of CR + CRh, duration of CRh, and duration of CR will be provided based on different censoring methods.

1. For subjects who had post treatment therapy before disease progression events or death due to disease progression, two methods will be performed:
 - Method 1: this subject data will be censored at the date of last disease assessment before starting post treatment therapy;

- Method 2: this subject's data will be considered as an event at the date of last disease assessment before starting post treatment therapy.
2. For subjects who are lost to follow-up without disease progression or death due to disease progression documented, last disease assessment (bone marrow and hematology lab collations) will be considered as an event.
 3. If a disease progression or death due to disease progression event occurred more than 91 days (3 cycles) from the last disease assessment (bone marrow collection or hematology lab collection), this subject will be censored at the date of last disease assessment prior to the disease progression or death due to disease progression event.

Details of the censoring method for sensitivity analyses of duration of response are provided below in [Table 5](#).

Table 5. Censoring Methods for Analyses of CR + CRh, CR, and CRh

Situation	Date of Progression/Date of Censor	Outcome
Post-treatment therapy initiated with no disease progression documented	Date of last disease assessment before initiating post-treatment therapy (bone marrow or hematology lab)	Method 1) Censored
Post-treatment therapy initiated with no disease progression documented	Date of last disease assessment before initiating post-treatment therapy (bone marrow or hematology lab)	Method 2) Event
Loss to follow-up without disease progression or death due to disease progression documented	Date of last disease assessment (bone marrow or hematology lab)	Event
Death or disease progression occurred after missing a scheduled disease assessments (disease progression or Death due to disease progression occurred > 91 days of last disease assessment)	Date of last disease assessment (bone marrow or hematology lab)	Censored

Overall Survival

Sensitivity analyses for OS will be provided based on different censoring methods as shown in [Table 6](#). OS analysis including all deaths collected in the extracted database will also be performed.

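### SAP Table 4 censors responders who start new therapy according to whether they later die of disease, so the Kaplan-Meier durations of CR and CR + CRh are biased

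*SAP*

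**What the plan says.** SAP 8.1.5 runs duration of CR from response to the "first date of relapse, clinical disease progression or death due to disease progression, whichever occurred earliest". Section 8.1.6 gives duration of CR + CRh the same end point. Both are estimated by Kaplan-Meier and both refer to Table 4, whose four rows work as follows.

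- **Row 1.** An event at the earliest PD date for "IWG disease progression (PD) or Clinical disease progression (CPD) on or prior to any post-treatment therapy and data cutoff date".
- **Row 2.** Disease death by the cutoff is an event at the death date, "regardless whether it occurred after any new post-treatment".
- **Row 3.** With no event and no new therapy, the subject is censored at the last disease assessment.
- **Row 4.** "Neither PD nor CPD nor Death due to disease progression but having post-treatment therapy on or prior to the data cutoff date" is censored at the start of that therapy.

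Section 8.1.5 adds: "The disease assessment data after the onset of any post-treatment therapy will not be included in the duration of CR analysis".

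Section 8.1.11 plans sensitivity analyses for subjects who start new therapy before progression or disease death. Under Method 1, "this subject data will be censored at the date of last disease assessment before starting post treatment therapy". Method 2 counts an event on that same date.

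Protocol 8.1.3.1.2 defines duration of response by recurrence or PD and has no rule for new therapy.

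**The concern.** Take two responders who start new therapy on the same day, both without prior PD or CPD. One dies of disease before the cutoff; the other does not. Row 2 keeps the first at risk through the new therapy until death. Row 4 removes the second on the day therapy starts. Of those who start new therapy, only the ones who will die of disease contribute time after it. Kaplan-Meier needs censoring that does not depend on what happens later, and here it does.

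There are two consequences. The curve is distorted by an amount that grows with the share of responders who move to other therapy. It is also unstable over time. SAP 6.1 sets a cutoff at each interim analysis, and the version table mentions second and third interim reports. A subject censored at therapy start in one report can be put back at risk from that date in the next, after a disease death.

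The same durations feed the subgroup analyses in 8.1.13, and duration of CR + CRh feeds the MRD analysis in 8.1.12. The SAP expects such subjects: 8.1.13 counts CR/CRh subjects who went on to post-treatment therapy.

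**Working it through.** The documents give no expected duration of CR or CR + CRh, so there is no figure to reproduce. The check has three parts. All inputs below are assumptions, not trial data.

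**1. Small example.** There are 12 responders. Eight have no new therapy: events at months 4, 7, 9, 11 and 14, censored at 18, 20 and 22. Four start new therapy at month 5: two die of disease at months 10 and 16, and two are event-free to month 24. The estimate is S(t) = product of (1 − 1/number at risk) over event times.

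| Rule | At risk at months 4, 7, 9 | S(9) | S(10) | S(16) |
|---|---|---|---|---|
| Table 4 | 12, 9, 8 | 11/12 × 8/9 × 7/8 = 0.713 | 0.611 | 0.306 |
| All four censored at month 5 | 12, 7, 6 | 11/12 × 6/7 × 5/6 = 0.655 | 0.655 | 0.393 |
| All four followed | 12, 11, 10 | 11/12 × 10/11 × 9/10 = 0.750 | 0.667 | 0.417 |

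Against censoring all four, Table 4 is higher early, because the two future deaths are held as event-free from month 5. It is lower later, because the two survivors add no time after month 5. The median is month 14 under all three rules; the difference is in the curve.

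The cutoff effect shows in the same data. Suppose all 12 responded on one date and are assessed up to a cutoff at month 9.5. Neither death has occurred, all four are censored at month 5, and S(9) = 0.655. At a month-24 cutoff S(9) becomes 0.713, although nothing new has been learned about months 0 to 9.

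**2. Simulation.** Relapse time R is exponential with rate ln 2 / median. New-therapy time N is exponential with rate h. Disease death after new therapy is N plus an exponential time with rate d. Follow-up C is uniform on 6 to 36 months. New therapy counts if N < R and N < C. There were at least 300,000 responders per scenario. Uniform censoring means everyone is censored at N.

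| Relapse median | h | Share starting | d | Table 4 median | Uniform censoring |
|---|---|---|---|---|---|
| 10 | 0.005 | 5% | 0.06 | 9.9 | 10.0 |
| 10 | 0.01 | 10% | 0.06 | 9.8 | 10.0 |
| 10 | 0.04 | 31% | 0.06 | 9.4 | 10.0 |
| 14 | 0.04 | 36% | 0.06 | 12.1 | 14.0 |

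In the third row the 24-month rate is 13% against 19%.

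To isolate the rule, set d equal to the relapse hazard, so that the true curve is known. With h = 0.04, uniform censoring and following everyone both return 10.0 and 14.0. Table 4 returns 9.3 for a true 10.0 and about 12.4 for a true 14.0. With the 10-month median its 24-month rate is 12%, against a true 2^(−2.4) = 19%.

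**3. Direction.** A further 54 scenarios used a true median of 8 or 12 months, 9% to 47% starting therapy, a post-therapy relapse hazard ratio of 0.5, 1 or 2, a median PD-to-death lag of 0, 3 or 6 months, and follow-up of 12 to 36 months. Relative to censoring everyone at therapy start, the Table 4 median ranged from about −20% to +10%. Relative to following everyone to disease death, it ranged from −0.2% to −32%. The upward shifts arise because a long lag from PD to death dates the event late.

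**The case against.** **Method 1 already exists.** It treats everyone who starts new therapy before progression alike, so a result free of this defect will be reported. That stands, and it softens the consequence. It does not repair the main median and confidence interval, which still follow Table 4.

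**The effect may be small.** This also stands. At about 10% starting therapy the median moves about 2% in the second simulation row, and roughly 5% or less in the 54 scenarios. A low share is plausible: the protocol allows venetoclax to continue without progression (5.1) and excludes candidates for early transplant (5.2.2).

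**The studies are descriptive.** SAP 9.0 plans no formal testing, so no error rate is at stake. The estimates are still biased.

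Three stronger readings are tempting and are not supported.

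- A reader might infer that row 2 contradicts the sentence dropping disease assessments after new therapy. It does not. Death is not a disease assessment, and the same paragraph names disease death as an event. The combination is asymmetric, since later relapse is ignored while later disease death counts, but it is not contradictory.
- A reader might infer that row 2 should go. It is the only row that makes disease death an event, so deleting it would also lose disease deaths in responders who never had new therapy.
- A reader might infer that the published durations must be too short, or that these are the trial's principal durability results. The direction depends on the PD-to-death lag and on the comparison rule. The SAP does not rank these endpoints, and the protocol's secondary objective is duration of response, counted from CR, CRi or PR.

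**Conclusion.** The point holds for responders who start post-treatment therapy without prior PD or CPD. Rows 2 and 4 together make their censoring depend on later disease death, so the Kaplan-Meier estimates of duration of CR and CR + CRh are biased as specified and can change retrospectively with the cutoff. That follows from the table itself and needs no assumption.

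The size does need assumptions, because the documents give neither the share starting new therapy nor the later hazards. For a 10-month relapse median and a disease-death hazard of 0.06 per month, the loss in the median runs from about 0.1 month at 5% to 0.6 month at 31%. For a 14-month median with 36% starting therapy it is 1.9 months. These all shorten the median; with a long PD-to-death lag it can instead lengthen relative to uniform censoring. The rule should be corrected, but the documents do not show that the reported durations are materially wrong.

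**What to change.** Make one rule that ignores later outcome primary for both durations.

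- **Row 2:** limit it to disease deaths on or before the start of post-treatment therapy. Disease deaths in responders with no new therapy stay events.
- **Row 4:** censor every responder who starts new therapy before PD/CPD, whatever happens later, either at the last disease assessment before it (existing Method 1) or at therapy start. State one. Say also that PD seen only after new therapy is handled this way; no row literally covers it now.
- **Sensitivity:** follow everyone after new therapy, count later PD/CPD and disease death, and censor the rest at their last assessment by the cutoff. Check first how complete post-therapy assessments are.

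Keep the endpoint to disease death; a move to all-cause death would be a separate decision.

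The primary change costs an edit to Table 4 and a rerun, with no new data. The downside is that some disease deaths after new therapy no longer count in the primary analysis; the sensitivity analysis shows them. Reporting the number of responders who started new therapy before PD would let readers judge how much the choice matters.

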8.1.6 Duration of CR + CRh

Duration of CR + CRh is defined as number of days from date that subject achieved CR + CRh to the first date of relapse, clinical disease progression or death due to disease progression, whichever occurred earliest. If a subject is still responding at the data cutoff date, then the subject's data will be censored. The disease assessment data after the onset of any post-treatment therapy will not be included in the duration of CR + CRh analysis. The detailed censoring rule is described in [Table 4](#). For each analysis dataset, the distribution of duration of CR + CRh will be estimated using Kaplan-Meier methodology. Median duration of CR + CRh with the corresponding 95% CI will be provided from Kaplan-Meier estimation. Duration of CR + CRh will be summarized for all subjects, subjects achieving CR, and subjects achieving CRh.

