- CRh: all of the following criteria are met: Bone marrow with $< 5\%$ blasts, peripheral neutrophils of $\geq 0.5 \times 10^3/\mu\text{L}$, and peripheral platelets $\geq 0.5 \times 10^5/\mu\text{L}$ **

* Transfusion independence is defined as the absence of any RBC or platelet transfusion during any consecutive 8 weeks during the treatment period.³⁹

** For a bone marrow sample collected before the last cycle of study treatment, the hematology lab results collected from the date of bone marrow sample collection up to Day 1 of a subsequent cycle of study treatment will be used for CRh analysis. For a bone marrow sample collected during or after the last cycle of study treatment, the hematology lab results collected within 14 days after bone marrow sample collection date will be used for CRh analysis.

Reporting of Results

All dosed subjects will be assessed for response to treatment based on the published guidelines. Assessments will be performed at Cycle 2 Day 1, Cycle 4 Day 1, and every 3 cycles thereafter for response assessment until two successive bone marrow samples document a CR. When additional bone marrow evaluations are routinely indicated for clinical management, additional collection of bone marrow aspirate and peripheral blood are strongly encouraged as these findings have the potential to define either remission status or potential progression of leukemia. NOTE: For subjects who achieve CR or CRi, MRD status may be determined.

Subjects will be assigned to one disease state for best IWG response assessment, achievement of protocol defined hematologic response, and minimal residual disease positivity at the time of the best response.

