8.1.7 Overall Survival (OS)

Time to death for a given subject will be defined as the number of days from the date of first dose of study drug to the date of the subject's death. All events of death will be included, regardless of whether the event occurred while the subject was still taking study drug, or after the subject discontinued study drug. If a subject has not died on or before the "Cutoff" date, and there is any data (survival follow-up, study visit, death date, etc.) confirming that the subject is still alive or dies after the "Cutoff" date, the data will be censored at the "Cutoff" date; otherwise the data will be censored at the date when the subject was last known to be alive.

For each analysis datasets, the distribution of OS will be estimated using Kaplan-Meier methodology. Median survival time with the corresponding 95% CI will be provided from Kaplan-Meier estimation.

OS will be summarized for all subjects, subjects achieving CR, subjects achieving CRh, and non-CR/non-CRh subjects.

8.1.8 Post Baseline Transfusion Independence Rate (RBC/Platelet) and Duration of Post Baseline Transfusion Independence

The transfusion data was designed to be collected during the treatment period and until the 30 day follow-up visit. Therefore, the evaluation period for the post baseline transfusion independence is from the first dose of study drug to the last dose of study drug + 30 days, disease progression (including clinical progression), or death, whichever is earlier. Thus, post baseline transfusion independence is defined as a period of at least 56 days (≥ 56 days) with no RBC or platelet transfusion during the evaluation period.

Post baseline transfusion independence rate will be estimated as the proportion of subjects known to achieve transfusion independence during the evaluation period. The corresponding 95% CI for transfusion independence rate will be provided based on the binomial distribution (Clopper-Pearson exact method).

In addition, the baseline transfusion independence rate, which is defined as the proportion of subjects who received no transfusion within 56 days prior to the first dose of study drug (Studies M14-358 and M14-387) or 28 days (Study M14-212) prior to the first dose of study drug, will also be summarized. An analysis based on the definition of baseline transfusion independence as 28 days on or prior to the first dose of study drug will also be performed for all studies.

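### SAP 8.1.6 splits duration of CR + CRh by a response status that can be reached after the clock has started, so the CR and CRh medians can differ even with equal durability

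*SAP*

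**What the plan says.** **Clock.** SAP 8.1.6 measures the "number of days from date that subject achieved CR + CRh to the first date of relapse", clinical progression or death due to progression. The date is that of the composite. First of the two is the natural reading, though the word first is not used.

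**Rows.** "Duration of CR + CRh will be summarized for all subjects, subjects achieving CR, and subjects achieving CRh". The section does not say whether the CRh row means CRh as best response or CRh at any time.

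**Neighbouring sections.**
- SAP 8.1.2 counts a CRh responder by best response: "CRh rate will be defined as the proportion of subjects who achieve CRh as the best response at any time point during the study".
- SAP 8.1.3 has the same three-row layout for time to response, "as well as for subjects with best response CR or best response of CRh will be summarized".
- SAP 8.1.7 reads as a partition: "OS will be summarized for all subjects, subjects achieving CR, subjects achieving CRh, and non-CR/non-CRh subjects".
- The CRh count thresholds in SAP 8.1.2 have lower limits only. An any-time CRh row would therefore take in nearly every CR subject.

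**Companion analysis.** SAP 8.1.5 starts at the CR date: "Duration of CR is defined as number of days from date that subject achieved CR to the first date of relapse".

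**Visits.** Protocol 5.3.3: "Assessments will be performed at Cycle 2 Day 1, Cycle 4 Day 1, and every 3 cycles thereafter for response assessment", until two successive marrows show CR.

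**Sensitivity analyses.** For duration, SAP 8.1.11 varies only the censoring and event rules. It names a duration of CRh without giving that analysis a population or start date.

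**The concern.** The rows are defined by something that happens after time zero. A subject in CRh at Cycle 2 Day 1 can be seen to reach CR at a later scheduled marrow only if still in remission then. The interval from CRh to CR is guaranteed event-free, and 8.1.6 counts it in the CR row. On the best-response reading, the same subject also leaves the CRh row because of having lasted, while a subject who relapses before the next marrow stays in it.

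Both effects lengthen the CR median relative to the CRh median. A reader who sets the rows side by side could conclude that partial count recovery gives a less durable remission when the data carry no such message. SAP 9.0 plans no formal testing, so the displayed medians are what readers will go by.

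**Working it through.** The documents give no duration, upgrade rate or CR + CRh count, so there is no figure of the plan's to reproduce. The check asks what the rows would show if durability were identical for everyone.

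**Inputs from the documents**
- Cycle length 28 days; marrows at Cycle 2 Day 1, Cycle 4 Day 1, then every 3 cycles.
- After a first response at Cycle 2 Day 1, the next marrow is 2 × 28 = 56 days later, then every 3 × 28 = 84 days: days 56, 140, 224, 308.
- Clock from first CR/CRh (8.1.6); CR-date clock for comparison (8.1.5).

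**Assumptions, not in the documents**
- Exponential duration from first CR/CRh, the same for all; true median 8 months (also 6 and 12).
- 40% of responders already in CR at first response.
- A fixed chance p of upgrade at each of the four visits while in remission; no censoring.

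**Step 1: closed form for a best-response CRh row.** Let relapse hazard be λ and upgrade hazard μ. A subject stays in the CRh row if relapse comes first, and the time to whichever comes first is exponential with rate λ + μ. So

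CRh-row median = ln 2 / (λ + μ) = true median × (1 − P(upgrade before relapse)).

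For a true median of 8 months and 10%, 20%, 40% or 60% upgraded: 8 × 0.9 = 7.2, 8 × 0.8 = 6.4, 8 × 0.6 = 4.8, 8 × 0.4 = 3.2 months.

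**Step 2: share upgraded on the protocol's visits.** With 30.44 days per month the median is 243.5 days, and the proportion still in remission at day v is 2^(−v/243.5): 0.853, 0.671, 0.529 and 0.416 at the four visits. The share of CRh-first subjects upgraded is p × [0.853 + (1−p) × 0.671 + (1−p)² × 0.529 + (1−p)³ × 0.416].
- p = 0.05: 0.05 × 2.324 = 12%.
- p = 0.20: 0.20 × 1.942 = 39%.

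**Step 3: simulated row medians in months, true median 8**

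| Upgrade chance per visit | CRh-first subjects upgraded | CR row | CRh row (best response) | All subjects |
|---|---|---|---|---|
| 0% | 0% | 8.0 | 8.0 | 8.0 |
| 5% | 12% | 8.9 | 7.2 | 8.0 |
| 10% | 22% | 9.5 | 6.4 | 8.0 |
| 20% | 39% | 10.0 | 5.0 | 8.0 |
| 40% | 61% | 10.1 | 2.9 | 8.0 |

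- At 20% per visit, a true median of 6 gives 7.7 against 3.9, and 12 gives 14.2 against 7.4.
- With only one upgrade visit at 10%, the rows are 8.2 and 7.8.
- On the any-time reading the CRh row stays at 8.0, but at 10% to 40% per visit the CR row is still 9.5 to 10.1.
- With 38 responders (assumed), the CR median exceeds the CRh median in 50% of simulated trials with no upgrades, and in 79%, 92% and 99% at 10%, 20% and 40% per visit.

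**Step 4: candidate remedies under the same null**
- Grouping by type of first response: 8.0 and 8.0 at every upgrade rate.
- Starting the CR row at the CR date: 8.0 under the exponential, but only because that law is memoryless. With a true median of 9 months and Weibull shapes 0.7 and 1.5, it gives about 10.5 and 8.2. Grouping by first response gives 9.0 for both rows in each case.

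**The case against.** **The text does not say best response.** SAP 8.1.2, 8.1.3 and 8.1.10 write those words and 8.1.6 does not. A reader might infer that 8.1.6 plainly removes every upgraded CRh responder from the CRh row. That is a well-supported inference, not stated text. On the any-time reading the CRh row loses nobody. This stands, but the CR row is lengthened on either reading, and the missing definition itself needs settling.

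**The size is assumed.** This stands. No upgrade rate is given, and the illustration has no censoring although SAP Table 4 censors at post-treatment therapy and at last assessment. Protocol 5.3.1.1 also expects unscheduled marrows on suspicion of improved response. The effect could be close to zero, so a statement that the CRh median will be too short by a particular percentage has no support.

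**The rows are descriptive.** This stands too. A reader might infer that they exist to show CRh is as durable as CR and so to justify the composite. No section gives that purpose.

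**SAP 8.1.5 already reports duration of CR from the CR date.** True, and its differing from 8.1.6 is not a contradiction: the two are differently defined quantities. But 8.1.5 does not repair a best-response CRh row, and step 4 shows that it is not a general comparator for CRh.

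**SAP 8.1.11 cannot be shown to repeat the problem.** Correct. It leaves the population for duration of CRh undefined, so the most that can be said is that it must be defined.

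**Conclusion.** The concern holds in a limited form. SAP 8.1.6 pairs a clock that most naturally starts at the first CR or CRh with groups formed by a status that can come later. The CR row then contains guaranteed event-free time for upgraded subjects. If the CRh row is best response, the likely reading, it also loses the longer-lasting CRh responders. No planned sensitivity analysis addresses either effect.

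With equal durability, the CR row was the longer in every scenario with upgrades that was examined. The gap runs from nothing with no upgrades, through 8.9 − 7.2 = 1.7 months at 5% per visit, to 10.0 − 5.0 = 5.0 months at 20%. These sizes rest on the assumed 8-month median, 40% CR at first response, four upgrade visits and no censoring. They are illustrations, not estimates for this trial. The all-subjects row and 8.1.5 are unaffected by this split.

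**What to change.** 1. In SAP 8.1.6, split duration of CR + CRh by the type of first CR/CRh-level response. CR-first and CRh-first subjects are each timed from that first response to the Table 4 event. Later-upgraded subjects stay in CRh-first, with their number stated.
2. Say explicitly that the 8.1.6 clock starts at the first of CR or CRh.
3. Keep the all-subjects row and 8.1.5 as they are.
4. In SAP 8.1.11, state the population and start date for duration of CRh, using the CRh-first group.
5. If best-response rows are kept for continuity with earlier interim reports, define them as such and label them descriptive and not for comparing the durability of CR and CRh.

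The cost is SAP wording and two extra or reprogrammed rows from dates already derived. The downside is less direct continuity with earlier interim outputs: SAP 2.1 records versions for the second and third interim reports.
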